The impact of device utilization was evaluated by measuring the total number of visits per patient by type (outpatient visits of low, moderate, and high complexity; ED visit without subsequent admission, general pediatric ward days, pediatric intensive care unit days) as determined via chart review. To adjust for the difference in sample size per group, the number of hospitalization days, acute office visits, and ED visits were reported descriptively as a *visit rate* calculated as the number of visits or hospital days/patient study months (number of patients in the group x number of study months). Four months of data were used for the calculation because the control group did not have any

hospitalizations during the technical month. The Kaplan-Meier method was used to estimate the proportion of each group that did not have any hospitalizations during the study period. A statistical comparison of the survival distribution was not conducted because the Kaplan-Meier method does not account for repeated episodes such as patients with more than one hospitalization.

A negative binomial regression model with Generalized Estimating Equations to handle repeated measurements was used to test the difference in hospital length of stay between groups. Model results were reported as regression coefficients, 95% Wald confidence intervals and p values. The negative binomial regression model was appropriate for this analysis, as the distribution of the outcome had greater variability than expected under a Poisson distribution. The sample mean of the outcome (4.3) was substantially smaller than its variance (102.3). Regression models were not tested for the number of acute office or ED visits because the incidence rate was too small for the inferential statistic. Analyses were conducted using SPSS (version 22.0) (IBM Corp. Released 2013. IBM SPSS Statistics for Windows, Version 22.0. Armonk, NY: IBM Corp). For all analyses, a p value < 0.05 was considered statistically significant.

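### The negative binomial GEE test of hospital length of stay relies on Wald inference with no stated small-sample method; at pilot size, with one total per patient and an uncorrected sandwich variance, it would reject a true null too often

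*Combined protocol and SAP*

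**What the plan says.** All of this is in the combined protocol and SAP.

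- **Test** (Analysis): "A negative binomial regression model with Generalized Estimating Equations to handle repeated measurements was used to test the difference in hospital length of stay" between the groups.
- **Inference** (Analysis): "Model results were reported as regression coefficients, 95% Wald confidence intervals and p values". The threshold is general: "For all analyses, a p value < 0.05 was considered statistically significant".
- **Reason for the model** (Analysis): "The sample mean of the outcome (4.3) was substantially smaller than its variance (102.3").
- **Software** (Analysis): "Analyses were conducted using SPSS (version 22.0"). No GEE options are given.
- **Other utilisation outcomes** (Analysis): "Regression models were not tested for the number of acute office or ED visits", because incidence was judged too low. The Kaplan-Meier curves are not compared statistically. Length of stay is therefore the only utilisation outcome tested by regression.
- **Size and allocation** (Participants): a single-centre pilot whose size was set by the eligible patients in the programme and the devices available. Allocation was 1.5:1, control to intervention, stratified by tracheostomy status. No number of patients is given.

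The text does not state the record unit (patient, patient-month or admission), the working correlation, the covariance estimator, how the dispersion was handled, or any small-sample correction. Table 1, which Data Collection cites for the outcome measures, is not in the text available and may define the record unit.

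**The concern.** Wald inference from GEE is a large-sample method, and the sample that counts is the number of independent patients. With few patients and a very skewed outcome, an arm with a low mean also tends to show a small empirical variance. The sandwich standard error is then too small exactly when the estimated ratio is extreme.

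The plan uses the mean and variance only to prefer the negative binomial to the Poisson. That choice addresses the variance function. It does not make a normal reference distribution adequate in a pilot.

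At stake is whether a p value below 0.05, or a 95% interval excluding no difference, means what it says for the one utilisation outcome given a regression test.

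**Working it through.** **Inputs from the plan.** Mean 4.3, variance 102.3, allocation 1.5:1, two-sided 5% (inferred from the 95% intervals), four months of observation.

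**Assumptions.** N = 20, 40 and 100, because no N is stated. The same distribution holds in both arms. The main case is one total per patient with an uncorrected sandwich.

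**1. The plan's overdispersion statement.** Variance/mean = 102.3/4.3 = 23.8. Negative binomial dispersion k = (102.3 − 4.3)/4.3² = 98.0/18.49 = 5.30. Proportion of zeros = (1 + 5.30 × 4.3)^(−1/5.30) = 0.55. The statement is consistent with its own figures.

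**2. Information available.** For one total per patient, the large-sample SE of the log ratio is √[(102.3/4.3²)(1/n₁ + 1/n₂)]. At N=40 (24 and 16) this is √(5.533 × 0.1042) = 0.76. A 95% interval then extends by a factor of exp(1.96 × 0.76) ≈ 4.4 in each direction.

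**3. Rejection of a true null, main case.** In each simulated trial the test is |log mean ratio|/SE > 1.96, with SE² = Σ over arms of Σ(y − ȳ)²/(n ȳ)². There were 40,000 trials per N. Trials with an all-zero arm were excluded (about 0.9% at N=20).

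| One total per patient | N=20 | N=40 | N=100 |
|---|---|---|---|
| Uncorrected sandwich | 19% | 13% | 8-9% |
| Bias-corrected sandwich, t(N−2) | 12.5% | 10.3% | 7.5% |
| Model-based SE, k correctly 5.3 | 7.5% | 6.9% | 5.6% |
| Model-based SE, dispersion fixed at 1 | about 36% | about 36% | about 36% |

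Capping totals at 122 days, the length of the four-month window, leaves the first row essentially unchanged (about 19-20% at N=20, 8% at N=100). The uncorrected 95% Wald interval covers a true ratio of 0.5 in 82%, 87% and 92% of trials if days fall proportionally.

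**4. Patient-month records.** A month holds at most 31 days. With mean 4.3 the variance cannot exceed 4.3 × (31 − 4.3) = 114.8, so 102.3 is 89% of the ceiling. An unbounded negative binomial is therefore unsuitable for months. A beta-binomial on 0-31 days, matched to 4.3 and 102.3, gives the following with an uncorrected sandwich:

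| Within-patient correlation | N=20 | N=40 | N=100 |
|---|---|---|---|
| 0 | 6.0% | 5.5% | about 5% |
| about 0.23 | 8.3% | 6.8% | 5.8% |
| about 0.47 | 11.3% | 7.1% | 5.3% |

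**5. Admission records.** With an assumed 0.5 to 2 admissions per patient and three assumed shapes for length of stay, rejection is about 16-40% at N=20 and 7-16% at N=100. At the smallest sizes some simulated trials could not be analysed and were left out, so these figures are only indicative.

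**6. The alternative test.** Permuting the studentised log rate ratio within two strata, with an all-zero arm counted as most extreme, rejects a true null in about 4-6% of trials across these N. Its power for a halved rate is about 6% at N=20, 12% at N=40 and 26% at N=100.

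**The case against.** The strongest reply is that both N and the sandwich are assumed, and that other reasonable readings are benign. That stands. Independent patient-months within the calendar are close to 5%, and so is a model-based standard error with the right dispersion once N approaches 100. A reader might infer that the test is inflated whatever the record unit. The documents do not support that, nor any single percentage as this trial's actual error rate.

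Two other inferences go too far.

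- **Selection on admission.** A reader might conclude that the test compares only admitted children. The text does not say so. Any analysis limited to admissions, or to one total per hospitalised patient, would condition on a post-randomisation event and miss avoided admissions. However, the unit is not stated, and the plan separately describes hospital days per patient study month and a Kaplan-Meier estimate of patients without hospitalisation.
- **Choice of window.** The plan says "Four months of data were used for the calculation because the control group did not have any" "hospitalizations during the technical month". A reader might infer that the GEE window was chosen from outcome data. That sentence follows the definition of the descriptive visit rate and concerns that calculation. Nothing ties it to the regression.

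It is also fair to say that this is a pilot with no stated primary hypothesis or decision rule, and that a better-calibrated test will have little power. Both are true, and they limit the importance of the point. They do not justify a 5% threshold that may not hold: the plan chose to test, and excess false positives are not power.

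**Conclusion.** The point holds in a conditional form. The plan applies a Wald test at p < 0.05 in a device-limited pilot with a highly overdispersed outcome and states no small-sample method. On the per-patient reading with an uncorrected sandwich, the true level is about two to four times nominal at N=20 to 40 (19% and 13%) and still 8-9% at N=100. On other readings it runs from near nominal to possibly worse, and the text does not let a reader tell which applies.

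This is a worthwhile, modest improvement to an exploratory result. It does not show that the reported result is wrong. Confidence is medium, because N, the record unit and the covariance estimator are all unknown.

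**What to change.** **Report** N per arm, the record unit, the covariance estimator and the handling of the dispersion for the GEE already run.

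**Add one analysis.** Test total hospital days (ward plus intensive care) per randomised patient, zeros included, with a log patient-months offset. Keep the negative binomial rate ratio as the estimate. Take the p value from a permutation test of the studentised log rate ratio, re-randomising within tracheostomy strata at the actual allocation. Fix in advance that an all-zero arm, in the data or in any relabelling, counts as most extreme, so that the test is always defined. A bias-corrected sandwich alone is not enough, since it still rejects 12.5% at N=20 in the per-patient case.

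**Present** it beside the reported GEE result, labelled exploratory and post hoc because the data have been seen.

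**Cost.** The data are already held and trial conduct does not change, but some programming is needed. The p value will probably be larger, and power is low: about 12% for a halved rate at N=40.

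### The one modelled hospital-use outcome is length of stay with no stated unit of analysis; if records are admissions, the comparison is conditional on a post-randomisation event and can move opposite to total hospital days

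*Combined protocol and SAP*

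**What the plan says.** All of this is in the Analysis section of the combined protocol and SAP.

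- The measure of impact is a per-patient total: "The impact of device utilization was evaluated by measuring the total number of visits per patient by type". The listed types include general ward days and PICU days.
- Rates per patient-month are descriptive only: "the number of hospitalization days, acute office visits, and ED visits were reported descriptively".
- Kaplan-Meier estimates of the hospitalisation-free proportion are given, but "A statistical comparison of the survival distribution was not conducted", because the method "does not account for repeated episodes such as patients with more than one hospitalization".
- Office and ED visits have no model: "Regression models were not tested for the number of acute office or ED visits".
- The remaining hospital outcome does have one, introduced as "A negative binomial regression model with Generalized Estimating Equations to handle repeated measurements". The plan states that this model "was used to test the difference in hospital length of stay between groups". The choice of distribution is justified by a sample mean of 4.3 and a variance of 102.3.

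The section does not say what one record is, what is repeated within a child, whether children with no admission appear as zeros, or whether the model has an exposure offset.

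**The concern.** The quantity modelled is not shown to be the quantity the plan says it measures. Length of stay ordinarily describes an admission, and where the section means person-time totals it uses other terms (ward days, hospitalisation days, visit rate). A single total per child would need no GEE. The only repeats the section names are children hospitalised more than once.

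If records are admissions, a child who is never admitted contributes nothing, and the arms are compared only among admissions. Admission comes after randomisation and can be affected by the device: under Procedure, the clinician chooses between treatment, clinic, ED and hospital on the data available, and the device adds to those data in one arm. The comparison is then no longer protected by randomisation, and averted admissions, a main route to benefit, drop out of the outcome. If the averted stays were mainly short ones, the mean of those remaining would rise and a benefit could read as harm.

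**Working it through.** **1. The plan's own figure.** Variance/mean = 102.3/4.3 = 23.8. This supports the statement that the outcome is far more variable than a Poisson count. The documents give no number of records, so the two moments themselves cannot be re-derived.

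**2. Do the moments identify the unit?** Inputs: m = 4.3, v = 102.3 (Analysis section).

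- *Records that include zeros.* A negative binomial matched to the moments has k = m²/(v − m) = 18.49/98.0 = 0.189 and P(0) = (k/(k + m))^k = (0.189/4.489)^0.189 = 0.55. About 55% of records would be zero. This assumes that the negative binomial is the true distribution.
- *Admissions of at least 1 day, negative binomial truncated at zero.* With mean 4.3 the variance is largest in the log-series limit (k → 0), at about 31. The stated 102.3 is out of reach, so an ordinary or truncated negative binomial would describe such stays poorly.
- *Admissions, any distribution.* Not excluded. Assume 30 stays: the sum is 30 × 4.3 = 129 and the sum of squares is 29 × 102.3 + 30 × 4.3² = 3,521. One stay of 55 days leaves 29 stays with sum 74 (mean 2.6) and sum of squares 3,521 − 3,025 = 496. That fits, but the single stay supplies 55/129 = 43% of the days and 50.7²/(29 × 102.3) = 87% of the squared deviation.
- *Child-months.* Values lie between 0 and 31, so the variance cannot exceed 4.3 × (31 − 4.3) = 114.8. The stated 102.3 is 89% of that ceiling (93% with 30-day months, ceiling 4.3 × 25.7 = 110.5). The mean implies 4 × 4.3 = 17.2 hospital days per child over the study. This is possible only if the days are concentrated in a few very heavy months.
- *Two periods per child* (the technical month and the following 3 months, which the section reports separately). The mean implies 2 × 4.3 = 8.6 days per child. Also possible.

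The moments do not settle the unit.

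**3. What follows if the unit is the admission?** The stays below are assumed, with equal-sized arms; none is trial data.

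| | Admissions | Total days | Mean stay |
|---|---|---|---|
| Control | six of 2 d, four of 10 d | 6×2 + 4×10 = 52 | 52/10 = 5.2 |
| Intervention, three 2-day stays averted | three of 2 d, four of 10 d | 3×2 + 4×10 = 46 | 46/7 = 6.57 |

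Ratio of totals 46/52 = 0.88; ratio of mean stays 6.57/5.2 = 1.26. With equal arms the ratio of totals is also the ratio of days per randomised child.

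A second assumed mix (60% 2-day and 40% 12-day stays), with 25%, 50% or 75% of the short stays averted, gives ×1.12, ×1.29 or ×1.55 for mean stay and ×0.95, ×0.90 or ×0.85 for total days. For the middle case: 60 days over 10 stays becomes 54 days over 7, so 7.71/6.0 = 1.29 and 54/60 = 0.90.

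The problem does not need short stays to be the ones averted. If half of each kind in the table were averted, total days would halve (3×2 + 2×10 = 26) while mean stay stayed at 26/5 = 5.2. The per-admission comparison would show no effect.

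**4. What follows if every child is included with zeros?** The outcome is then hospital days per child or per child-period. It is not conditional on admission, and averting any stay lowers it. Only the label and the missing specification remain at fault.

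**The case against.** A reader might infer that the test was run on admissions and is therefore conditional on being admitted. The documents do not establish that. Layouts with several records per child and every child included remain open: two reporting periods per child, separate ward and PICU records, or admission rows plus a zero row for each never-admitted child. The remark about repeated episodes explains why the Kaplan-Meier curves were not compared; it does not define the GEE records. The choice of a model that allows zeros is itself some evidence that zeros were present, as is the truncated-distribution check above. Poor fit to positive stays is thus a fault only if zeros are absent. Table 1, cited under Data Collection for outcome measures, is not in the text available and may define the outcome.

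A reader might also infer that this is the only p value on hospital use. The section lists t, Mann-Whitney, Chi-square and Fisher tests without naming their variables, and any of them could have been applied to days per child or to any admission. What can be said is that length of stay is the only hospital-use outcome with a named model.

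The descriptive rates and Kaplan-Meier proportions, which cover all patients, would let a careful reader notice a reversal. They carry no named comparison between arms, however, and the reader would still not know what the model's p value compares. The study is a pilot with a sample set by availability, and the text shown names no primary outcome, which limits how much weight the model must bear.

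These objections remove any claim that the analysis was conditional. They leave the mismatch between the outcome measured and the outcome modelled, and the missing unit.

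**Conclusion.** The point holds conditionally. The plan measures impact as ward and PICU days per patient but names a between-group model only for length of stay, without the unit, the treatment of never-admitted children or an offset. Read in its ordinary sense, the wording permits a comparison among admissions selected after randomisation, and such a comparison can miss or reverse a change in total days.

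The size in this trial is unknown. The 12% fall against a 26% rise is an illustration that rests on invented stays, on equal arms, and on the assumption that the device averts mainly short stays, which the documents do not say. The mean and variance pull in both directions: the negative binomial form favours zeros, while the child-month ceiling makes that particular layout strained. The point is still more than a missing detail, because a clearly better outcome, the plan's own per-patient measure in all randomised children, is available from data already held.

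**What to change.** Make the modelled outcome total hospital days (ward plus PICU) per randomised child over the observation period, with zero for each child never admitted. Use a negative binomial with a log follow-up-time offset; with one record per child, GEE is not needed for repeats. Report admissions per child and days per admission descriptively, as components of that total. State the record unit and the offset explicitly.

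If the existing model already included every child with zeros, by child or by period, say so and rename the outcome hospital days per child (or per child-period); no re-run is then needed to remove conditioning.

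The cost is a wording change and, at most, one re-run on data already collected. The drawback is that many children may have zero days, so the interval may be wider than a per-admission one.

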Evaluating the Value of Telehealth for Care of Children With Medical Complexity
Clinicaltrials.gov Identifier: NCT02849938
Unique Protocol ID: CCCMCTeleMed

Study Protocol and Statistical Analysis Plan

Last Revised: September 29, 2016

Participants

This study was designed as a single center, randomized, non-blinded pilot study. Sample size was determined by number of eligible patients enrolled in the Coordinated Care for Children with Medical Complexity (CCCMC) program at our institution as well as number of devices that were available for the pilot. Inclusion criteria included: patients aged 1 month to 18 years, currently enrolled in the CCCMC program; parent consent; at least one English-speaking parent; and in-home Wi-Fi connectivity. Children enrolled in the CCCMC program met the following criteria: 3 or more body systems requiring active management; technology dependent or full support to complete activities of daily living; and moderate or severe neuromotor delays, or intellectual disability. Children were excluded from this pilot study if caregivers expressed an inability to comply with study requirements. Participants were randomized 1.5:1 with stratification based on tracheostomy status to control group or intervention group (Research Randomizer, Urbaniak). This stratification was done to attempt to balance patient contact between the groups based on the assumption that patients with tracheostomies may require more frequent contact with the CCCMC team. Clinicians in the CCCMC program included a pediatrician and pediatric nurse practitioner. This study and subsequent revision was approved by the Advocate Health Care Institutional Review Board and registered at ClinicalTrials.gov (Identifier: NCT02849938).

Telehealth Device

The selected telehealth device (TytoHome™) is an FDA-approved, handheld, mobile device designed for capture and transmission of ear, throat, and skin images, heart and lung auscultations including heart rate detection, and temperature data taken by infrared transdermal thermometer. The device required pairing with an iOS tablet (Apple iPad mini 4) for transmission via wireless network for live-interactive clinician connection. Caregivers used the telehealth device to perform non-invasive medical examinations in the home for remote view by a clinician. TytoCare™ provided the telehealth devices and the iPad minis that were used in the pilot.

Procedure

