Enrolled parent caregivers provided informed consent during a home visit for study initiation. For those in the intervention group, members of the TytoCare™ team were present along with study team to explain the use of the telehealth device and iPad mini; set up the components and connect them to in-home Wi-Fi; and answer any questions. The home was assessed for adequate internet connectivity and supplemental connectivity was provided by TytoCare™ if needed.

All caregivers were instructed to contact their clinician by telephone or email as usual when they had any health concerns. If an exam was deemed necessary by the clinician, patients in the control group were referred for an in person encounter, whereas caregivers of patients in the intervention group were directed to connect the telehealth device if appropriate. During a telehealth visit, the clinician conducted a 2-way, live, interactive

audio/video visit with the patient. If clinically indicated the clinician would direct the caregiver to use the telehealth device to provide temperature, lung sounds, heart sounds, oropharyngeal exam, skin exam and/or ear exam. Regardless of the group, the clinician would base direction for necessary treatment, referral to an ED, clinic visit or hospitalization based on available data. In addition, telehealth visits were scheduled in advance for routine care if indicated such as for post-discharge care, follow-up for a particular concern, or to maintain familiarity with the telehealth device (technical practice).

Data Collection

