Direct cost for each encounter was obtained from our institution's financial accounting system (EPSi), which was used to calculate direct costs per study group and encounter type (not including overhead costs such as cost of the telehealth device or connectivity). For the intervention group, a telemedicine visit was equated to a Level 4 return encounter in the outpatient setting. Direct cost savings were calculated as the absolute difference between the two study groups. To adjust for the difference in group sample size, the

encounter direct cost was multiplied by the visit rate and the adjusted cost rates were described for each group. Potential cost savings were calculated using clinician input on the visit types that were likely prevented as a result of the telemedicine device.

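### The direct cost saving omits the device, tablet and connectivity, which only the intervention arm uses, so it is gross of the intervention's equipment cost

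*Combined protocol and SAP*

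**What the plan says.** The cost method is at the end of the Analysis section. Encounter costs come from the institution's accounting system and are summarised by group and encounter type, "not including overhead costs such as cost of the telehealth device or connectivity". Telehealth visits are given a proxy price: "For the intervention group, a telemedicine visit was equated to a Level 4 return encounter in the outpatient setting". The saving is then defined: "Direct cost savings were calculated as the absolute difference between the two study groups". Because the groups differ in size, the "encounter direct cost was multiplied by the visit rate and the adjusted cost rates were described for each group".

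The visit rates are defined a little earlier in the same section, where "the number of hospitalization days, acute office visits, and ED visits were reported descriptively" as counts over patient study months, using four months of data. A telehealth visit rate is not named. A second figure, potential cost savings, rests on clinicians' judgement of which visits were prevented, and it is not said to charge any intervention cost.

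Two other sections show what the intervention consists of. Telehealth Device: "The device required pairing with an iOS tablet (Apple iPad mini 4) for transmission via wireless network for live-interactive clinician connection". The manufacturer supplied both items. Procedure, on setting up intervention homes: "The home was assessed for adequate internet connectivity and supplemental connectivity was provided by TytoCare™ if needed".

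**The concern.** Leaving overhead out of a between-group cost difference is harmless when it is common to both arms, because it cancels. The two items named as overhead here are not common. They are part of the randomised intervention, are placed in each intervention home, and have no counterpart in the control arm. Calling them overhead does not change that.

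The trial's title promises an evaluation of the value of telehealth. A difference that counts encounters possibly avoided, but not the equipment used to avoid them, cannot by itself show that telehealth saves money. It would also not carry over to a program that has to obtain the equipment itself. Nothing in the documents adds these costs back, plans a sensitivity analysis with them, or gives a break-even value.

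**Working it through.** **Is there a figure to reproduce?** No. The documents give no encounter cost, equipment price, saving, group size or count of telehealth visits. The check is therefore algebra plus an illustration on stated assumptions.

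**Inputs from the documents**
- Excluded: overhead, with device and connectivity as named examples (Analysis). The tablet is not named, but the device needs it and the same supplier provided it (Telehealth Device), so its exclusion is inferred.
- Charged: encounters in both arms, with a telehealth visit priced as a Level 4 return encounter (Analysis).
- Period for the rates: 4 months (Analysis).
- Allocation 1.5:1 (Participants).
- In-home Wi-Fi is an eligibility requirement (Participants), so only added connectivity is specific to the intervention arm, and c may be zero in some homes.

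**Formula.** Per patient-month, let G be the gross saving (control minus intervention encounter cost). Then

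net saving = G − (K/L + c) + v × (P − T) + D

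where K is device plus tablet cost per patient, L the months over which it is spread, c monthly connectivity, v telehealth visits per patient-month, P the Level 4 price, T the true direct cost of a telehealth visit, and D the difference (control minus intervention) in other excluded overhead.

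- K/L + c cannot be negative and falls on one arm only. Alone, its omission favours telehealth.
- v × (P − T) has either sign. If P exceeds T, the proxy overcharges telehealth and works against it.
- D is unknown. If in-person care carries more overhead, D is positive and also works the other way.
- If telehealth visits do not enter the adjusted cost rate, G charges nothing for them. The proxy term then becomes −v × T, a further omission in telehealth's favour. The named visit rates leave this open.

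**Size of K/L + c.** All prices are assumptions: K = $300 to $1,500, c = $0 to $50.

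| L (months) | Low | High |
|---|---|---|
| 4 | 300/4 + 0 = $75 | 1,500/4 + 50 = $425 |
| 12 | 300/12 + 0 = $25 | 1,500/12 + 50 = $175 |
| 36 | 300/36 + 0 = $8.3 | 1,500/36 + 50 = $91.7 |

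The 4-month row writes the hardware off over the study period and is the upper bound. Longer lives are more realistic for reusable equipment.

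**Could the proxy cancel it?** With D = 0, the omission is offset exactly when v × (P − T) = K/L + c. For an omission of $75, the Level 4 price would have to exceed the true visit cost by 75/0.5 = $150, 75/1 = $75 or 75/2 = $37.50 per visit at v = 0.5, 1 or 2. The documents give neither v nor P − T, so this can be neither confirmed nor excluded.

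**Why the correction is per patient-month.** K/L + c is on the scale of the size-adjusted rates. The defined saving is an absolute group difference, and it is not clear whether that is taken before or after size adjustment. With 1.5:1 allocation and equal cost per patient, unadjusted totals would differ by 1 − 1/1.5 = 33% of the larger arm's total.

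**The case against.** The strongest reply has four parts.

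1. **Telehealth examinations are not free in this analysis.** A reader might infer that the intervention arm's examination cost is set to zero. The plan does not do that: each telemedicine visit is given the price of a Level 4 return encounter. What is missing is equipment and connectivity. This stands, subject to the open question of whether those visits enter the adjusted rates.

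2. **The direction of the final figure is not shown.** The Level 4 proxy may overcharge telehealth, and some telehealth visits were held only to keep caregivers practised with the device (Procedure). The exclusion is worded as overhead in general, with device and connectivity as examples, so overhead of in-person care also appears to be left out. This stands. Only the effect of this one omission has a known sign.

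3. **Materiality is unproven.** Costs include ward and intensive care days, which may dwarf equipment cost, and every price above is assumed. This stands as a limit on the claim. It is also a reason to report a break-even value, which needs no equipment price.

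4. **The exclusion is disclosed, the measure is labelled direct cost, and this is a pilot with no planned test of cost.** A comparison limited to direct encounter cost is a recognisable perspective, and no passage claims net savings. The outcome table cited under Data Collection is not in the available text and may define the measure further. This lowers the severity but does not remove the point. The result is still called a saving, and a parenthesis in the methods does not make a gross difference a net one.

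**Conclusion.** The point holds in a limited form. The planned direct cost saving excludes intervention-only equipment and connectivity, and is therefore gross of them. Taken alone, the omission favours telehealth by K/L + c per intervention patient-month. Under the assumed prices that is about $8 to $425: $75 to $425 if written off over the 4 study months, and $8 to $92 over 36 months. These amounts illustrate scale and are not estimates from the trial. Inclusion of the tablet rests on inference.

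Two stronger conclusions might be drawn, and the documents support neither. One is that the reported saving is shown to be biased towards telehealth overall: the proxy visit price and the other excluded overhead could push the other way, and neither is quantified. The other is that equipment is the largest cost specific to the intervention arm: no prices or visit counts are given, so the inputs cannot be ranked. It is also not known whether any conclusion about cost would change. This is a worthwhile, inexpensive improvement to the analysis and reporting.

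**What to change.** 1. Label the present figure as an encounter-cost difference excluding intervention equipment and connectivity, and label the potential cost savings figure in the same way.
2. Add a size-adjusted net figure per patient-month that charges the intervention arm with device, tablet and connectivity (including any supplied by the manufacturer) over a stated life, with the 4-month study period as the upper bound on the monthly charge.
3. Report the break-even equipment cost per patient-month. It equals G if the Level 4 price is right and other overhead is set aside, and G + v × (P − T) otherwise.
4. Vary the Level 4 proxy in a sensitivity analysis, and state how visits held only for device practice are costed.
5. Define a telehealth visit rate and make sure it enters the adjusted cost rate. Say whether the saving is the size-adjusted difference.
6. Claim a cost saving only from the net figure.

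The cost is a price list and a little more analysis, with no change to trial conduct. The reported saving is likely to look less favourable once equipment is charged.
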